**Diagnostic assessments**

7. Current evidence (by central laboratory) or history of inhibitor to FVIII with a titer  $\geq$  0.6 Bethesda unit (BU).

**Other Exclusions**

8. Known hypersensitivity to the drug substance, excipients, or mouse or hamster protein.

**5.3 Lifestyle Considerations**

No restrictions are required.

**5.4 Screen Failures**

Screen failures are defined as participants who consent to participate in the clinical study but are not subsequently entered in the treatment phase of the study. A minimal set of screen failure information is required to ensure transparent reporting of screen failure participants to meet the Consolidated Standards of Reporting Trials (CONSORT) publishing requirements

and to respond to queries from regulatory authorities. Minimal information includes demography, screen failure details, eligibility criteria, and any serious adverse event (SAE).

Individuals who do not meet the criteria for participation in this study (screen failure) may be rescreened once, and repeat the screening procedures/laboratory tests provided that all screening procedures/laboratory tests are performed within the 8-week screening period. Rescreened participants should be assigned a new participant number.

## 6. Study Intervention

Study intervention is defined as any investigational intervention(s), marketed product(s), placebo, or medical device(s) intended to be administered to a study participant according to the study protocol.

### 6.1 Study Intervention(s) Administered

All treatment decisions for identifying appropriate prophylactic treatment regimens should be guided by clinical judgment based on the approved SmPC and the individual participant characteristics and treatment response:

Treatment	Every 5 days	2x/week	Every 7 days
Intervention Name		Jivi	
Type		Biologic	
Dose formulation		Ampule	
Duration of intervention	Up to 100 ED, regimen as per investigator decision		
Unit dose strengths	500, 1000, 2000, or 3000 IU/vial		
Dosage Level(s)	45-60 IU/kg Every 5 days The total recommended maximum dose/injection is approximately 6000 IU (rounded up to vial size).	40 IU/kg Two times per week	60 IU/kg Every 7 days The total recommended maximum dose/injection is approximately 6000 IU (rounded up to vial size).
Route of Administration	IV injection		
IMP and NIMP	IMP (Jivi)		
Sourcing	Provided by the Sponsor		
Packaging and Labeling	Jivi will be provided in glass vials with a prefilled syringe. Each glass vial will be labeled as required per country requirement.		
Current Name / Former Name	Commercial name: Jivi / BAY 94-9027		

ED=exposure day, IMP=Investigational medicinal product, NIMP= Non investigational medicinal product

**Treatment of bleeds**

All bleeding events that occur in participants receiving prophylactic infusion after the start of treatment (Visit 2) will be treated with Jivi as outlined in the package insert (SmPC). If a bleed occurs on a day of the planned injection, the participant should treat the bleed instead of receiving the scheduled prophylactic infusion.

The infusion schedule with Jivi is not affected by the treatment of bleeds, eg, if a participant treats a bleed on Sunday and is due to infuse his prophylactic dose on Monday, he will still receive the scheduled infusion. If a repeated treatment for the bleed is required, the dose administered on the scheduled infusion day may be modified to ensure the participant receives appropriate treatment.

**6.2 Preparation/Handling/Storage/Accountability**

Instructions for the preparation of study interventions can be found in the leaflet for using Jivi.

All study interventions will be stored at the investigational site in accordance with Good Clinical Practice (GCP) and Good Manufacturing Practice (GMP) requirements and the instructions given by the clinical supplies department of the sponsor or its affiliates.

Special storage conditions and a complete record of batch numbers and expiry dates can be found in the sponsor's study file; the site-relevant elements of this information will be available in the investigator site file. On the day of receipt, the responsible site personnel will confirm receipt of study intervention via IxRS.

1. The investigator or designee must confirm appropriate temperature conditions have been maintained during transit for all study intervention received and any discrepancies are reported and resolved before use of the study intervention.
2. Only participants enrolled in the study will receive study intervention and only authorized site staff will supply or administer study intervention. All study intervention must be stored in a secure, environmentally controlled, and monitored (manual or automated) area in accordance with the labeled storage conditions with access limited to the investigator and authorized site staff.
3. The investigator, or the head of the institution (where applicable) is responsible for study intervention accountability, reconciliation, and record maintenance (i.e., receipt, reconciliation, and final disposition records).
4. Further guidance and information for the final disposition of unused study interventions are provided in a separate document.

### **6.3 Measures to Minimize Bias: Randomization and Blinding**

This is an open-label study, and no randomization or masking will be performed.

Participants will be identified by a unique participant number with 9 digits once the ICFs are signed. The first 5 digits will identify the country and study site, the last 4 digits are assigned to the participant of the specific site in increasing order.

### **6.4 Study Intervention Compliance**

Participant compliance with study intervention will be assessed at each visit.

Used and unused vials of study medication will be returned to the clinic at every site visit for accounting. Any discrepancies between actual and expected amount of returned vials must be discussed with the participant at the time of the visit, and any explanation must be documented in the source records.

The electronic patient diary (EPD) will be used to assess the participant's compliance with the treatment schedule/dose, and to reconcile study medication inventory. The EPD will be used to record date and time of self-administration of study intervention for prophylaxis as well as every bleeding episode with details of the bleeding and administered intervention. Data on the EPD will be transmitted on a regular basis.

The EPD will be reviewed at visits and at regular contacts with the participant during the study.

### **6.5 Prior and Concomitant Therapy**

Any medication or vaccine (including over-the-counter or prescription medicines, vitamins, and/or herbal supplements) that the participant is receiving at the time of enrollment or receives during the study must be recorded along with:

- Reason for use
- Dates of administration including start and end dates
- Dosage information including dose and frequency

The Medical Monitor (Study Medical Expert) should be contacted if there are any questions regarding concomitant or prior therapy.

Bleeds which occur during the screening period (Screening visit until Visit 2) will be treated with the participant's previous FVIII product.

All medications and blood products required by the participant after the informed consent is signed, including FVIII products other than study intervention, will be listed in the appropriate CRF. All concurrent prescription and non-prescription medications including over-the-counter and alternative preparations (including herbal remedies, vitamins, and health food supplements), antibiotics and pain medications being administered starting at least 3

months previous to the study will be recorded in the CRF at screening and throughout the treatment and follow-up periods.

The participant should not be taking any other investigational drug while receiving treatment with Jivi.

Medications which cause a bleeding diathesis (for example, Aspirin® or any acetylsalicylic acid) should be avoided in individuals with hemophilia, except as specifically prescribed by a treating physician. Low dose Aspirin should not be discontinued in participants who have been identified to be at risk for cardiovascular events. The decision to prescribe non-steroidal anti-inflammatory drugs, Cyclooxygenase-2 (COX-2) inhibitors, or brief courses of corticosteroids to treat pain or acute synovitis is at the discretion of the treating physician.

Inhaled or topical steroid medications (as for the treatment of asthma or eczema) are allowed. Brief courses of prednisone/methylprednisolone (< 14 days) for treatment of disorders such as synovitis, asthma, etc. are at the discretion of the treating physician. For any participant requiring longer courses of corticosteroids or use of other immunomodulatory treatment, the investigator should notify the sponsor.

## **6.6 Dose Modification**

This protocol allows some alterations from the currently outlined dosing schedule, but the maximum dose must not exceed approximately 60 IU/kg for every 5 days and every 7 days treatments and approximately 40 IU/kg for 2x/week treatment, and for patients with overweight, the dose per injection should not be higher than approximately 6000 IU, rounded up to full vials. Dose adaptations according to participant needs and at the investigator's discretion are allowed within the approved dose range and rounding up to full vials which may result in slightly higher dosages.

## **6.7 Intervention after the End of the Study**

After completion of the study, treatment with study intervention will end. Subsequent treatment will be mutually agreed upon by the participants and the investigator.

# **7. Discontinuation of Study Intervention and Participant Discontinuation/Withdrawal**

## **7.1 Discontinuation of Study Intervention**

- Inhibitor development

Any inhibitor development ( $\geq 0.6$  BU/mL, confirmed) is considered a SAE.

Discontinuation of study intervention due to a high titer inhibitor development (titer  $> 5$  NBU/mL) should be considered by the investigator if the investigator believes that it is in the best interest of the participant and/or if bypassing agents are needed to treat bleeds. Participants who discontinue study intervention due to inhibitor development cannot continue in the study and will be withdrawn.

- Planned major surgery during the study

If the participant has a planned elective surgery during the study, the investigator and sponsor will determine if the participant can continue in the study and if any change in participant management is needed.

See the SoA for data to be collected at the time of intervention discontinuation and for any further evaluations that need to be completed.

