## **7.2      Participant Discontinuation/Withdrawal from the Study**

A participant who withdraws is one who discontinues from a clinical study for any reason. The participant will not suffer any disadvantage as a result.

- A participant may withdraw from the study at any time at his own request without giving reasons, or may be withdrawn at any time at the discretion of the investigator for safety, behavioral, compliance, or administrative reasons..
- At the time of discontinuing from the study, if possible, an early discontinuation/final visit should be conducted, as shown in the SoA. See SoA for data to be collected at the time of study discontinuation and follow-up and for any further evaluations that need to be completed.
- The participant will be permanently discontinued both from the study intervention and from the study at that time.
- If the participant withdraws consent for disclosure of future information, the sponsor may retain and continue to use any data collected before such a withdrawal of consent.
- A participant must be withdrawn from the study if the development of an inhibitory antibody to Jivi that neutralizes activity sufficiently to interfere with effective treatment or requires use of a bypassing agent to treat bleeds.
- A participant must be withdrawn from the study if he fails to comply with scheduled appointments for the study-related evaluations and with EPD data entry to an extent that compromises collection of critical data.
- A participant must be withdrawn from the study if significant concurrent illness or deterioration occurs in the participant's condition, including laboratory values that the investigator deems to be incompatible with the participant's continued safe participation in the study.

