## 8. Study Assessments and Procedures

- Study procedures and their timing are summarized in the SoA and visit description Section 10.4. Protocol waivers or exemptions are not allowed.
- Immediate safety concerns should be discussed with the sponsor immediately upon occurrence or awareness to determine if the participant should continue or discontinue study intervention.
- Adherence to the study design requirements, including those specified in the SoA, is essential and required for study conduct.
- All screening evaluations must be completed and reviewed to confirm that potential participants meet all eligibility criteria.
- Procedures conducted as part of the participant's routine clinical management (e.g., blood count) and obtained before signing of the ICF may be utilized for screening or baseline purposes provided the procedures met the protocol-specified criteria and were performed within the time frame defined in the SoA.
- If deemed necessary for an individual participant, the investigator or designee, at his/her discretion, may arrange visits in addition to the scheduled study visits. Unscheduled visits will be documented in the eCRF.

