### **FVIII inhibitor**

FVIII inhibitor testing will be done according to the Nijmegen modified Bethesda assay. A positive inhibitor test is defined with a threshold of  $\geq 0.6$  BU at the central laboratory.

If an inhibitor is detected as part of scheduled testing, the investigator will be notified. Repeat testing within 2 to 4 weeks of notification should be obtained. Any positive test will be confirmed by a second different sample. Only after confirmation of the positive result, the inhibitor has to be reported as SAE.

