### 8.3.1 Time Period and Frequency for Collecting AE and SAE Information

All AEs and SAEs will be collected from the signing of the informed consent form (ICF) until the end of the final study visit at the time points specified in the SoA (Section [1.3](#)).

Medical occurrences that begin before obtaining informed consent but are diagnosed at screening or during the screening period (e.g., abnormal lab values) will be recorded on the Medical History/Current Medical Conditions section of the case report form (CRF), not the AE section.

All SAEs will be recorded and reported to the sponsor or designee immediately and under no circumstances should this exceed 24 hours, as indicated in Section [10.3](#). The investigator will submit any updated SAE data to the sponsor within 24 hours of it being available.

Investigators are not obligated to actively seek AE or SAE after conclusion of the study participation. However, if the investigator learns of any SAE, including a death, at any time after a participant has been discharged from the study, and he considers the event to be reasonably related to the study intervention or study participation, the investigator must promptly notify the sponsor.

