## 10. Supporting Documentation and Operational Considerations

### 10.1 Appendix 1: Regulatory, Ethical, and Study Oversight Considerations

#### 10.1.1 Regulatory and Ethical Considerations

- This study is a post-approval regulatory requirement according to the EMA Guidelines for a new marketed FVIII and will be conducted in accordance with the protocol and with the following:
  - Consensus ethical principles derived from international guidelines including the Declaration of Helsinki and Council for International Organizations of Medical Sciences (CIOMS) International Ethical Guidelines
  - Applicable International Council for Harmonization (ICH) Good Clinical Practice (GCP) Guidelines
  - Applicable laws and regulations
- The protocol, protocol amendments, ICF, SmPC, and other relevant documents (e.g., advertisements) must be submitted to an IRB/IEC by the investigator and reviewed and approved by the IRB/IEC before the study is initiated.
- Any amendments to the protocol will require IRB/IEC approval before implementation of changes made to the study design, except for changes necessary to eliminate an immediate hazard to study participants.
- The investigator will be responsible for the following:
  - Providing written summaries of the status of the study to the IRB/IEC annually or more frequently in accordance with the requirements, policies, and procedures established by the IRB/IEC
  - Notifying the IRB/IEC of SAEs or other significant safety findings as required by IRB/IEC procedures
  - Providing oversight of the conduct of the study at the site and adherence to requirements of ICH guidelines, the IRB/IEC, and all other applicable local regulations

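### For a high-titer inhibitor that needs bypassing agents, Protocol 7.1 only asks the investigator to consider stopping Jivi, while Protocol 7.2 makes stopping mandatory

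*Protocol*

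**What the plan says.** Protocol 7.1 (Discontinuation of Study Intervention) first makes any confirmed inhibitor of at least 0.6 BU/mL an SAE. For a high titer, above 5 NBU/mL, it then says that discontinuing study intervention "should be considered by the investigator if the investigator believes that it is in the best interest of the participant and/or if bypassing agents" have to be used for bleeds. It adds that participants who stop because of an inhibitor are withdrawn from the study.

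Protocol 7.2 (Participant Discontinuation/Withdrawal from the Study) says: "A participant must be withdrawn from the study if the development of an inhibitory antibody to Jivi that neutralizes activity sufficiently to interfere". What must be interfered with is the effectiveness of treatment. The same sentence then adds a second trigger: "or requires use of a bypassing agent to treat bleeds". It gives no titer. On the effect of withdrawal, 7.2 says: "The participant will be permanently discontinued both from the study intervention and from the study at that time".

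Three other provisions bear on how such a case would be handled:

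- Protocol 8: "Immediate safety concerns should be discussed with the sponsor immediately upon occurrence or awareness to determine if the participant should continue or discontinue study intervention".
- Protocol 8.2.1, FVIII inhibitor: "Only after confirmation of the positive result, the inhibitor has to be reported as SAE".
- Protocol 8.3.1: "All SAEs will be recorded and reported to the sponsor or designee immediately and under no circumstances should this exceed 24 hours".

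**The concern.** Protocol 2.3 describes an inhibitor as the most serious adverse event to be expected with FVIII replacement, and inhibitor development is the primary endpoint. The rule for what happens to the participant afterwards should read the same wherever it appears. Here the section devoted to stopping the drug states the weaker rule, in a case where the next section leaves no choice.

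What is at stake is participant management and protocol compliance. A site that looks up drug discontinuation will go to 7.1, find a decision left to judgement, and find no pointer to the mandatory rule. There is no data monitoring committee (Protocol 1.1; SAP 4.4), so the decision rests with the site and the sponsor.

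**Working it through.** No figure is involved, so the check sets the two rules side by side.

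**Step 1. Compare the elements of each rule.**

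| Element | Protocol 7.1 | Protocol 7.2 |
|---|---|---|
| Object | Stopping Jivi | Withdrawal from the study, which also stops Jivi permanently |
| Titer | Above 5 NBU/mL | None stated |
| Trigger | Participant's best interest, and/or bypassing agents needed | Inhibitory antibody to Jivi interferes with effective treatment, or a bypassing agent is required |
| Strength | To be considered by the investigator | Mandatory |

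The need for a bypassing agent is named in both sections, so the overlap is explicit.

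**Step 2. Apply both rules to each case.**

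| Case | 7.1 | 7.2 | Result |
|---|---|---|---|
| Above 5 NBU/mL, bypassing agent needed | Consider stopping | Must withdraw and stop Jivi | Different strength, same trigger |
| Above 5 NBU/mL, effective treatment impaired, no bypassing agent | Consider stopping, if in best interest | Must withdraw and stop Jivi | Different strength |
| Above 5 NBU/mL, neither | Consider stopping, if in best interest | No rule on the inhibitor | Consistent |
| 0.6 to 5 BU/mL, either 7.2 trigger met | Discontinuation sentence is silent | Must withdraw and stop Jivi | 7.1 incomplete, not contradictory |

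**Step 3. Test whether drug and study are separate decisions.** If 7.1 governed only the drug and 7.2 only study participation, there would be no mismatch. The text excludes this in both directions. Under 7.2, withdrawal ends study intervention for good. Under 7.1, stopping because of an inhibitor ends study participation. It is one decision, stated at two strengths.

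**Step 4. Test compliance in each direction.** A site that follows 7.2 stops Jivi, which is one permitted outcome of considering it, so 7.1 is satisfied too. A site that follows 7.1 and decides against stopping breaches 7.2.

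**Step 5. Look for another provision that settles it.** None was found.

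- Protocol 7.1.1 (temporary discontinuation) covers elective major surgery only.
- Protocol 8.2.1 directs that Jivi be stopped for the immune response associated with anti-PEG antibodies. That is a different case, in which normal recovery on the previous product rules out an inhibitor.
- Protocol 4.4 (premature termination) concerns the whole trial.
- Protocol 6.1 says that bleeds are treated with Jivi, but does not say what follows when they cannot be.
- Protocol 8 requires discussion with the sponsor but gives no criterion for the decision.

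**The case against.** The strongest objection is that this is no true conflict. Being told to consider stopping is not permission to continue, and 7.2 sets the floor. The sections are almost adjacent under one heading, and a precedence clause is needed only when two rules cannot both be obeyed. In addition, 7.1 properly covers high-titer inhibitors without a bypassing agent, where discretion is right. A participant who needs bypassing agents is already outside the treatment plan in Protocol 6.1. A confirmed inhibitor reaches the sponsor as an SAE within 24 hours, immediate safety concerns go to the sponsor in any case, and 7.2 lets the investigator withdraw a participant for safety at any time.

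Most of this stands. The rules can be obeyed together, and the safeguards make an unnoticed departure unlikely. Two things remain. By naming bypassing agents among the reasons merely to consider stopping, 7.1 treats as discretionary a case that 7.2 does not. And the safeguards bring the case to the sponsor's attention without making the two sentences agree. The SAE route for the inhibitor itself also opens only on confirmation, although the Protocol 8 discussion need not wait for that.

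A reader might infer that the plan allows sites to keep such participants on Jivi. The documents do not support that, because 7.2 forbids it without exception. A reader might also infer that the primary endpoint is compromised. It is not: inhibitors are identified by assay threshold and repeat testing, whatever is decided about treatment, and SAP 4.2 keeps dropouts in all safety analyses.

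**Conclusion.** The concern holds as an inconsistency of wording in a participant-safety stopping rule. For a titer above 5 NBU/mL with bypassing agents needed, 7.1 is discretionary and 7.2 mandatory, and 7.1 does not point to 7.2. Following 7.2 resolves it in practice, so this is a minor point, worth correcting because correction is nearly free.

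The affected cases should be rare. Protocol 2.3 reports no new or confirmed inhibitors in the clinical studies, and this trial excludes anyone with a current or past inhibitor of at least 0.6 BU. The documents do not say what share of inhibitors would be high-titer and need a bypassing agent, so no expected number of cases is offered. The conclusion rests on the text of the two sections and does not depend on that number.

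**What to change.** Replace the discontinuation sentence in Protocol 7.1 with the two sentences below. The words in quotation marks are 7.2's own, and the marks themselves would be dropped:

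> Study intervention must be discontinued, whatever the titer, if an inhibitory antibody to Jivi neutralizes activity sufficiently to interfere with effective treatment "or requires use of a bypassing agent to treat bleeds" (see Section 7.2). For any other high-titer inhibitor (> 5 NBU/mL), discontinuation should be considered if the investigator judges this to be in the participant's best interest.

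The first sentence uses 7.2's term, an inhibitory antibody to Jivi, and not simply an inhibitor, so that the two sections cover the same cases. The second keeps the discretion that 7.1 properly gives elsewhere. The 7.1 sentences on SAE status and on withdrawal after stopping stay as they are, as does 7.2.

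The cost is two sentences. Protocol 10.1.1 says: "Any amendments to the protocol will require IRB/IEC approval before implementation of changes made to the study design". The change should therefore go into the next amendment and does not need one of its own. The SAP, sample size and data collection are unchanged.
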